Design Overview: This study will randomize 140 African American menthol cigarette smokers to receive either menthol cigarettes (i.e. continue smoking menthol cigarettes) or non-menthol cigarettes for a four week period. At the conclusion of the four week period, participants will attempt to quit smoking all cigarettes and will return for follow-up over a 6 month period. Tobacco use, nicotine use, motivation and self-efficacy to quit, nicotine craving and withdrawal measures and support for a ban on menthol cigarettes will be assessed during the study period. Urine cotinine concentrations will be measured at each visit. The primary outcome in this study is time from cessation to the first smoking lapse.

Subjects: In order to be eligible for this study, subjects must: 1) be African American (based on self-identification); 2) smoke primarily menthol cigarettes (greater than 80% of cigarettes smoked are menthol); 3) be between the ages of 18 and 64; 4) Smoke on average, at least 8 cigarettes per day for a period longer than 1 year and 5) express an interest in quitting smoking (rate themselves ≥ 7 on a 10 point scale assessing motivation to quit smoking). Subjects will be excluded if they have: 1) A current unstable medical / psychiatric condition as determined by self-report; 2) Substance abuse within six months of beginning the study based on self-report; 3) Regularly use any form of nicotine or tobacco other than cigarettes or 4) Are pregnant or breast feeding based on self-report (subjects will

be given a urine pregnancy test at the screening visit with pregnancy later in the study and breast feeding based on self-report).

As the risks associated with the study procedures are small, all medical assessments are based on self-report (except for a urine pregnancy test at screening).

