Recruitment will be limited to African American smokers for several reasons. Menthol cigarette use is particularly prevalent in the African American community with 80% of African Americans reporting menthol cigarettes as their usual choice (2). Additionally, data suggest that greater difficulty in cessation of menthol cigarettes (vs. non-menthol cigarettes) may be limited to African Americans (2) and therefore methods to improve cessation rates from menthol cigarettes are particularly relevant to this population. Since our preliminary study suggests that few menthol smokers spontaneously attempt to quit when asked to abstain from menthol cigarettes, we will only enroll those interested in smoking cessation.

African American menthol smokers will be recruited via the use of flyers and advertisements in local newspapers and neighborhood newspapers with a high African American readership or on internet resources such as Craigslist. If additional advertisement becomes necessary, radio or television advertisements may be utilized. Our research team has considerable experience recruiting smokers and we have determined which advertisement strategies are most effective.

Implementation Plan

Overview: Each subject will attend a screening visit to determine if they are eligible for the study. If subjects are eligible, they will be randomized to either the 'menthol' or 'non-menthol' group. Subjects will continue smoking in their normal manner for one week after the screening visit to gather information on their baseline smoking patterns after which they will attend a baseline visit. Week 0 will be considered their quit date, therefore the baseline visit will be week -4 (i.e. 4 weeks before their target quit date). Additional visits will be scheduled at week -3, week -2 and week 0 (i.e. 1, 2 and 4 weeks subsequent to the baseline visit). Follow up visits will occur at weeks 1, 2, 4, 6, 8, 12 and 26. The procedures occurring during each of these visits are described below.

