Screening Visit: All subjects will undergo a screening visit prior to enrollment at which written informed consent will be obtained and eligibility will be verified. Medical and psychiatric history will be obtained via subject report. Baseline questionnaires assessing smoking history and nicotine dependence will be administered. Exhaled carbon monoxide (CO) will be measured to confirm that they are smokers (CO \geq 8 ppm) with a NicCheck performed (with a cut-off of ≥ 5) for those who state that they smoke \geq 8 cigarettes per day but for whom CO is less than 8 ppm (e.g. they didn't smoke that morning, they are coming from a smoke free work environment, etc.). Subjects that qualify and are interested in participating will be asked to maintain a smoking diary for the duration of the study and will be scheduled for the baseline visit.

Baseline and Pre-Quit Visits: Smoking behavior subsequent to the screening visit will be determined as will subjects' level of craving, withdrawal, perceived health risk, motivation and self-efficacy to quit smoking and support for a menthol ban. At the baseline visit subjects will be told their randomization and given appropriate product (i.e. menthol or non-menthol cigarettes, based on randomization) at no cost to them for a total of 4 weeks. Subjects will be given a quantity of cigarettes equivalent to approximately 120% of their average daily use based on smoking diaries collected at the baseline visit or at pre-quit visits up to a maximum of approximately 1.5 packs per day. Since cigarettes packs generally contain 20 cigarettes, these percentages are approximations subject to rounding. This amount is chosen in case smoking increases as a result of switching to non- menthol and to allow for flexibility in scheduling subjects for subsequent visits (i.e. if a visit is delayed by several days, subjects will still have product). Subjects will be asked to smoke only study product for the 4 week period following the baseline visit. They will be given no specific instructions regarding using medicinal nicotine (i.e. nicotine patch, gum) or the use of e-cigarettes but will be asked to record any instances

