At all visits, subjects will be asked to provide a urine sample. The urine will be used to measure cotinine concentrations and may in the future also be used to measure other markers related to smoking menthol cigarettes (such as other nicotine metabolites, menthol concentrations, tobacco toxicants, etc.). Subjects will also be asked to bring in their smoking diary in which they are to record cigarettes smoked as well as any other tobacco or nicotine products used (including e-cigarettes).

Follow up visits: Starting at Week 0 (quit date); subjects will attend follow up visits at weeks 1, 2, 4, 6, 8, 12 and 26. At each of these visits subjects will be asked if they have smoked at all since their previous visit. Exhaled carbon monoxide (CO) will be measured with an exhaled CO less than 8 ppm and a urine cotinine concentration of less than 50 ng/ml confirming abstinence (16). Smoking diaries will be used to determine time to lapse (time from their quit attempt until any smoking occurs) and time to relapse (time from their quit attempt until the first day of seven consecutive days that a cigarette is smoked).

Subjects will be paid \$20 for the screening visit, \$30 for each of the 7 visits between week 0 and week 12 with a \$100 bonus if they complete all visits up to week 12 and have complied with study related procedures. We anticipate that it will be more difficult to retain subjects through the 6 month visit; therefore subjects will receive \$60 for that visit. Since it is imperative that subjects honestly report any smoking during the study (in order to calculate time to lapse), payment during the cessation phase will not be contingent on successful abstinence. Subjects that relapse and resume smoking during the study will still be eligible to continue in the study. However, subjects that fail to follow study procedures (e.g. provide urine samples, fill out questionnaires, etc.) will be removed from the study.

Data and Safety Monitoring Plan:

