Time to lapse: The primary outcome, time to lapse following the week 0 visit, will be evaluated using a two-sided log-rank test. Since drop-outs could be more likely to lapse, we will perform two tests: one censoring drop-outs at the time of their last visit, and one considering drop-outs as lapsed at the time of their last visit. Randomization of 140 subjects should balance the groups with respect to potential confounding factors, and therefore no adjustment for other factors is planned. The same procedure will be used for the secondary outcome of time to relapse.

Other outcomes: Several continuous outcomes will be measured at baseline and subsequent time points, such as motivation and self-efficacy to quit, support for a menthol ban, severity of craving, perceived health risk, urinary cotinine concentrations, and exhaled CO. We will first calculate the change in each subject's outcome from baseline to the week 26 visit, and compare the study groups using two-sided, two sample t-tests. This will provide a straightforward comparison of whether cessation of menthol use affects long-term nicotine use and perceptions. Second, we will use analysis of variance (ANOVA) with repeated measurements to further analyze trends over all visits in the study period, with group, time, and interaction effects. This would identify more precisely when particular changes took place, or if any group differences emerged around the quit attempt but diminished by the end of the study. Changes in tobacco product use within groups will be summarized qualitatively and by descriptive statistics such as proportions.

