Power and Sample Size: Our primary outcome is time to lapse. Previous studies have found that during a cessation attempt most participants lapse within one week, at a median of 2-3 days after their quit attempt (35, 36). We plan on enrolling 140 subjects randomized 1:1 with an approximately 15% post-randomization visit dropout rate, leaving 120 subjects with data on time to lapse. This gives us over 80% power to detect a 1.7-fold difference using a significance cutoff of 0.05. We believe that such a difference would be a meaningful indicator of smoking success. The 1.7 fold difference in time to lapse is substantially smaller than is typically seen with medication studies. For example, an analysis by Shiffman et al (J Consult Clin Psychol 2006;74:276-85) found that the median duration of abstinence (i.e. time to lapse) was 6 days for active nicotine patch and 2 days for placebo. That would correspond to a 3 fold difference. Directly comparable data for other interventions is not available, however in a study comparing placebo to five different pharmacotherapy options (i.e. bupropion, nicotine lozenge, patch, bupropion + lozenge, patch + lozenge), the time until 50% of participants in the placebo group lapsed was approximately 6 days whereas the time for all other groups (except for nicotine lozenge) the time until 50% of participants lapsed was over 20 days (Japuntich et al. J Consult Clin Psychol 2011;79:34-42), an over 3-fold difference. Likewise, we

would have 80% power to detect an effect size of 0.6 in continuous secondary outcomes (i.e. a difference in group means of 0.6 times the outcome's standard deviation). Since it is not clear what the smallest difference is that would be important to detect, we believe that this sample size will be able to detect a meaningful difference.

Data and Record Keeping:

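### Does relying on expected balance to justify an unadjusted log-rank test cost the trial power that it should have kept?

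*Combined protocol and SAP*

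**What the plan says.** The primary outcome is time from the quit date to the first lapse, tested with a two-sided log-rank test under two rules for drop-outs. On covariates, Data Analysis (Time to lapse) says: "Randomization of 140 subjects should balance the groups with respect to potential confounding factors, and therefore no adjustment for other factors is planned". Time to relapse is handled in the same way. No adjusted or stratified analysis of these outcomes appears elsewhere.

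Power and Sample Size expects 120 of 140 randomised subjects to supply time-to-lapse data and states: "This gives us over 80% power to detect a 1.7-fold difference using a significance cutoff of 0.05". It illustrates what fold means with median abstinence of 6 and 2 days in a patch trial: "That would correspond to a 3 fold difference".

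Candidate covariates exist before allocation. Under Screening Visit: "Baseline questionnaires assessing smoking history and nicotine dependence will be administered". Cigarettes per day is part of eligibility in the Subjects paragraph ("Smoke on average, at least 8 cigarettes per day for a period longer than 1 year"); the summary of protocol changes lowers that threshold to 5, which does not affect whether the measure is available. The Implementation Plan overview places allocation after eligibility is established, and allocation is disclosed later: "At the baseline visit subjects will be told their randomization and given appropriate product".

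**The concern.** The stated reason answers only half of the question. Expected balance protects against confounding. It does not bear on precision: in a time-to-event comparison, leaving out a variable that predicts the event can cost power even when the arms are perfectly balanced. The plan holds two plausible predictors of lapse, nicotine dependence and cigarettes per day, both recorded before randomisation and at no extra cost.

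The stated power is only a little above 80%, so a few free points would be worth having. If adjustment reliably supplied them, ruling it out on grounds of balance alone would be a missed opportunity in the primary analysis.

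**Working it through.** **1. The plan's own power.** Inputs from Power and Sample Size: 140 randomised 1:1, about 15% drop-out, a 1.7-fold difference, two-sided 5%. 140 × 0.85 = 119, which the plan gives as 120. Assume that all 120 lapse and read 1.7 as a hazard ratio under exponential times.

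- Schoenfeld: Φ(√120 × ln 1.7 / 2 − 1.960) = Φ(2.906 − 1.960) = Φ(0.946) = 82.8%.
- Freedman: Φ(√120 × 0.7/2.7 − 1.960) = Φ(2.840 − 1.960) = Φ(0.880) = 81.1%.

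The stated figure of over 80% reproduces for the unadjusted test that is planned.

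**2. Validity without adjustment.** With 70 per arm, the standardised difference in any one covariate has standard deviation 2/√140 = 0.169, so it exceeds 0.2 in absolute value in about 24% of trials. Such chance imbalance does not invalidate the test, because its 5% error rate is taken over all possible allocations, imbalanced ones included. Simulated type I error of the log-rank test at 60 per arm was 5.2 to 5.3%.

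**3. What adjustment would buy.** The documents do not say how strongly any screening measure predicts lapse, so the strength is assumed and shown as a range. The simulation had 60 per arm, exponential times with a control median of 2.5 days (middle of the plan's 2 to 3), rounding up to whole days, 182 days of follow-up and a ratio of 1.7 for each smoker. Log-risk varied between smokers with SD 0, 0.3 or 0.5. One covariate correlated with risk as shown; a second correlated 0.4 with the first and added nothing. The adjusted test was a log-rank score with arm-specific linear adjustment for both. There were 30,000 replicates per power setting and 100,000 per null setting.

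The adjusted test's type I error was 5.6 to 5.8%, so part of any nominal gain is a looser test. The last two columns hold both tests at a true 5%.

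| Risk SD | Correlation | Power at nominal 5%: log-rank / adjusted | Both held at 5%: log-rank / adjusted | Change when held at 5% (points) |
|---|---|---|---|---|
| 0 | – | 81.2 / 81.4 | 80.4 / 79.8 | −0.6 |
| 0.3 | 0 | 75.2 / 75.7 | 74.5 / 73.8 | −0.7 |
| 0.3 | 0.2 | 75.4 / 75.9 | 74.7 / 74.1 | −0.6 |
| 0.3 | 0.3 | 75.5 / 76.1 | 74.7 / 74.6 | −0.1 |
| 0.3 | 0.5 | 74.6 / 75.9 | 73.9 / 74.2 | +0.3 |
| 0.3 | 0.8 | 75.2 / 77.3 | 74.7 / 75.9 | +1.2 |
| 0.5 | 0 | 67.4 / 67.8 | 66.5 / 65.6 | −0.9 |
| 0.5 | 0.2 | 67.0 / 67.5 | 66.1 / 65.5 | −0.6 |
| 0.5 | 0.3 | 66.8 / 67.9 | 65.9 / 66.0 | +0.1 |
| 0.5 | 0.5 | 67.2 / 69.3 | 66.1 / 67.0 | +0.9 |
| 0.5 | 0.8 | 66.9 / 72.0 | 66.2 / 70.2 | +4.0 |

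Monte Carlo noise in the changes is a few tenths of a point. The lower starting power at SD 0.3 and 0.5 comes from the assumed variation between smokers. If 1.7 is instead read as a population-average ratio, the size-matched figures at correlation 0.5 are 79.3 / 79.5 (SD 0.3, +0.2) and 77.4 / 78.5 (SD 0.5, +1.1).

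Separately written code for the same design (12,000 power and 16,000 null replicates) gave size-matched changes of −0.8 (SD 0), +0.2 (SD 0.3, correlation 0.5), +1.0 (SD 0.5, correlation 0.5) and +3.9 (SD 0.5, correlation 0.8).

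**4. Variations.** With one covariate instead of two, the size-matched changes were −0.4 (SD 0), +0.4 (SD 0.3, correlation 0.5) and +1.1 (SD 0.5, correlation 0.5). Under the plan's two drop-out rules (140 randomised, 15% lost at random after week 0), nominal gains were 0.2 to 2.0 points with drop-outs censored and 0.6 to 1.7 with drop-outs counted as lapsed, before any correction for size.

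**The case for a change.** The strongest opposing case uses a covariate-adjusted Cox model in which a single measured covariate carries all the variation in risk. With the treatment effect set so that the log-rank test keeps about its planned power, power rises from 81% to 83% at a covariate hazard ratio of 1.22 per SD, from 82% to 87% at 1.35, and from 82% to 90% at 1.49. Such gains are real if the trial records so good a predictor. But those figures assume risk is measured without error, they are not size-matched, and nothing in the documents supports the strengths used. Once part of the risk is unmeasured, as with a dependence score and a cigarette count, the gains shrink to those in the table.

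The thin margin also deserves an answer: by Schoenfeld's formula, power reaches 80% at 112 lapses and is 76% at 102. A shortfall in lapses is not what adjustment repairs, however, and the documents point the other way. The summary of protocol changes raises approved enrolment from 200 to 250 so that at least 120 subjects complete. Someone who lapses early and leaves later still counts as an event, so lapses could exceed 120. As an illustration, the same formula gives Φ(√140 × ln 1.7 / 2 − 1.960) = 88% with 140 lapses and 92% with 160. The documents give neither the number randomised nor the number of lapses.

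What stands is that the plan's sentence does not mention power. A fuller rationale would read better, but it would change no result.

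**Conclusion.** The concern does not hold. The reason given is sound for the purpose it serves, the unadjusted log-rank test is valid, and its stated power reproduces at 81 to 83%. With both tests held at 5%, replacing it by a two-covariate adjusted test changes power by between −0.9 and about +1 point for correlations with lapse risk from 0 to 0.5, with break-even near 0.3. A larger gain, up to 4.0 points in the settings examined, needs a correlation of about 0.8 and wide variation in risk between smokers.

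This rests on assumed risk SDs of 0 to 0.5, exponential lapse times and near-complete lapse. Since the sign of the effect turns on a prognostic strength that the documents do not give, the choice is a preference between two acceptable tests. The plan has made it in advance and matched its power statement to it. Nothing needs to change.

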of using any nicotine or tobacco product. If subjects ask specifically about e-cigarettes, they will be told they can be used as long as they report their use at the next visit. Since e-cigarettes would be available to smokers were menthol cigarettes to be banned, to most closely mimic naturalistic conditions we will not ask subjects to abstain from e-cigarettes. However, since the risks of e-cigarette use are unclear as are their impact on cigarette cessation, we will also not encourage their use. In order to approximate what would likely occur were a menthol ban to be enacted, no specific instructions will be given to subjects about how to effectively quit but subjects will be encouraged to call the Smoking Quitline to obtain support for their cessation attempt. At each visit, exhaled carbon monoxide concentrations will be measured and subjects will complete questionnaires assessing craving and withdrawal symptoms, smoking urges, perceived health risk, and motivation to quit smoking. Subjects will also complete a food diary to assess menthol intake from sources other than cigarettes. A questionnaire assessing level of support for a menthol ban will be assessed at baseline, the week 0 (i.e. their quit day) visit and post-quit visits. At the baseline visit subjects will set a quit date which will be the day of their week 0 visit (i.e. they are not to smoke after the visit). If subjects wish to quit smoking the next day, that will also be allowed. At each visit, subjects will return all unused study product. In order to encourage smokers to bring back all unused product, subject payment will increase by the market value of the brand of cigarettes that they received (i.e. currently about \$8 per pack for most brands) based on how much they return. Since subjects will be provided cigarettes during the first month, they will not receive additional compensation (although parking will be provided). Returned cigarettes may be provided to the same subject as part of their subsequent supply but will not be used for any other subjects.

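### Motivation to quit is tested across arms mainly at week 26 without regard to smoking status, so if quit rates differ the contrast mixes quitting with motivation

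*Combined protocol and SAP*

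**What the plan says.** All references are to the combined protocol and SAP.

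- **Data Analysis, Other outcomes.** The continuous outcomes are given by example, "such as motivation and self-efficacy to quit, support for a menthol ban, severity of craving" and others. The first analysis is to "calculate the change in each subject's outcome from baseline to the week 26 visit" and "compare the study groups using two-sided, two sample t-tests". The second is an ANOVA to "analyze trends over all visits in the study period, with group, time, and interaction effects". Neither is restricted or stratified by smoking status.
- **Baseline and Pre-Quit Visits.** At each visit, "subjects will complete questionnaires assessing craving and withdrawal symptoms, smoking urges, perceived health risk, and motivation to quit smoking".
- **Subjects.** The only description of a motivation scale for this trial is in the entry criteria: a self-rating of at least 7 "on a 10 point scale assessing motivation to quit smoking".
- **Follow up visits.** There are seven visits after the quit date, at weeks 1, 2, 4, 6, 8, 12 and 26. Smoking since the last visit is asked each time, and subjects who relapse may stay in the study, so abstainers and smokers are followed together.
- **Specific Aims.** Hypothesis (a) is that switching improves cessation. Hypothesis (b) is that switching before cessation raises motivation and self-efficacy to quit.

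Nowhere do the documents say how an abstinent subject answers the motivation item, how that answer is scored, or whether such subjects are analysed separately.

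**The concern.** Motivation to quit smoking has a plain meaning for someone who smokes. For someone who has stopped, it is unclear what the item asks. Such a subject might mark the top (fully committed), mark the bottom (nothing left to quit) or leave it blank. The plan puts all of these into the same mean.

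This would be only noise if the arms had equal numbers of quitters. The trial's main hypothesis is that they do not. Quitting happens after randomisation, so randomisation does not balance it. The motivation contrast then carries a component produced by the difference in quitting, with a sign set by response habits. At one extreme, a switch that helped people quit could be reported as lowering their motivation. Leaving blanks out does not solve this, because it compares only continuing smokers, a group selected by a post-randomisation outcome.

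**Working it through.** **1. The plan's own figure.** Power and Sample Size claims 80% power for 0.6 SD in continuous outcomes. With 60 per arm and two-sided alpha 0.05, power = Φ(0.6/√(2/60) − 1.96) = Φ(3.29 − 1.96) = 90.8%. The stated 80% is not reproduced: it needs only 44 per arm. The claim is conservative and does not bear on this point.

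**2. How many subjects could be abstinent.** The same section says that "most participants lapse within one week, at a median of 2-3 days after their quit attempt" and plans for a 1.7-fold difference. Assuming a constant hazard, the lapse-free share at day t is exp(−ln2 × t/median). The medians are 2 to 3 days in controls and, multiplied by 1.7, 3.4 to 5.1 days in switchers.

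| Visit | Controls | Switchers |
|---|---|---|
| Week 1 (day 7) | 8.8-19.8% | 24.0-38.6% |
| Week 2 (day 14) | 0.8-3.9% | 5.8-14.9% |
| Week 4 (day 28) | 0.01-0.2% | 0.3-2.2% |

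By week 26 the model leaves essentially no one continuously lapse-free. Subjects who lapse and later stop again could be abstinent then, but the documents give no figure. Week 26 quit rates are therefore assumptions: 5% vs 10% and 10% vs 20%.

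**3. Size of the artefact.** If continuing smokers have the same mean in both arms:

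artefact = (difference in quit proportion) × (quitters' mean score − smokers' mean score)

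Assume a smokers' mean of 8.

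- 10% vs 20%, all quitters mark 1: 0.10 × (1 − 8) = −0.70 points.
- 10% vs 20%, all mark 10: 0.10 × (10 − 8) = +0.20.
- 5% vs 10%, all mark 1: 0.05 × (−7) = −0.35. All mark 10: 0.05 × 2 = +0.10.
- Equal quit rates and equal answering: 0.

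**4. Against the spread actually tested.** Scoring quitters far from smokers also widens the SD. With a smokers' SD of 2, the variance in an arm with quit proportion p is 4 + p(1 − p) × 49 when quitters mark 1. This gives 8.41 at 10% and 11.84 at 20%, average 10.1, SD 3.18. So −0.70 points is 0.70/3.18 = 0.22 SD.

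**5. False significance.** Simulated trials used 60 per arm, baseline scores of 7-10, and follow-up motivation Normal(8, 2) rounded and clipped to 1-10 with the same distribution in both arms. The correlation between motivation and abstinence was 0 to 0.4, and change was compared by t-test. At 10% vs 20%:

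| Quitters' answer | Mean arm difference | p < 0.05 |
|---|---|---|
| All mark 1 | −0.7 to −0.8 | 22-27% |
| Half mark 1, half mark 10 | between the extremes | 8-9% |
| All mark 10 | +0.1 to +0.2 | 6-10% |
| Blank | 0 to about −0.1 | 4-5% |

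At 5% vs 10%, false significance is 10-13% if all mark 1 and 5-7% otherwise.

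**6. What the pre-quit visits offer.** Subjects are to stop smoking after the week 0 visit, so nearly all are still smokers when they answer at weeks -3, -2 and 0. At 60 per arm, the effect detectable with 80% power is (1.96 + 0.84) × √(2/60) = 0.51 SD, inside the plan's 0.6 SD.

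**The case against.** **The item may be valid for abstainers.** The questionnaire is not in the documents, and the 10-point scale is described only as an entry criterion. A reader might infer that abstinent subjects have no valid score. The documents support only that the plan defines none; an item that also covers staying quit would weaken the point. Nor is it clear that a person one week into an attempt has nothing left to quit. This objection stands.

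**Post-quit measurement is partly inferred.** The sentence on motivation questionnaires is under Baseline and Pre-Quit Visits, and the follow-up text does not list the item. But the planned change to week 26 requires it, so the inference is sound.

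**The largest figures belong to a test the plan does not run.** At week 1 rates of about 14% vs 32%, with all quitters marking 1, the artefact is about −1.2 points and roughly half of simulated trials are falsely significant. A reader might carry that rate over to the plan. The only planned t-test is at week 26; week 1 enters only as one visit in the ANOVA, which was not simulated. Nor does −1.2 points equal the plan's 0.6 SD effect: against the widened SD of the change scores it is about 0.35-0.39 SD.

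**Quitters may be few, and the extreme answer is unlikely to be universal.** The plan's lapse figures imply almost no continuous abstainers by week 4, so they do not show material distortion at every post-quit visit. With mixed answers the excess false significance is slight. This limits the size, not the logic.

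**The plan wants long-term perceptions, and its ANOVA already includes the pre-quit visits.** Both are true. But the ANOVA pools those visits with the post-quit ones, and the leading test uses week 26 alone.

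**Conclusion.** The point holds as a secondary-outcome issue of uncertain, probably modest size. The plan's leading test of motivation is placed where quitting and motivation cannot be separated, and no scoring rule is given for abstainers. If quit rates differ, the sign of the contrast depends on how quitters answer: about −0.8 to +0.2 points at an assumed 10% vs 20%. The quit rates, the smokers' mean of 8, the SD of 2 and the answering patterns are all assumptions, and every quitter marking 1 is the extreme case.

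A reader might infer that the trial's main conclusion is at risk. It is not: the log-rank analysis of time to lapse does not use the motivation score.

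Week 0 also suits hypothesis (b) better. Its subject is the effect of switching before cessation, and week 0 ends the switching period. The preliminary study made the parallel comparison, baseline to week 4 of switching (5.3 vs 6.3). Two limits remain. In that study 3 of 31 subjects tried to quit during the four weeks, so week 0 is free of the problem for nearly all subjects, not all. And if the entry scale is also the outcome scale, a subject entering at 7 or more can rise by at most 3 points at any visit.

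**What to change.** In Data Analysis, Other outcomes, give motivation to quit its own rule:

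1. The main between-arm comparison is change from baseline (week -4) to week 0, by the two-sample t-test already planned.
2. The repeated-measures analysis for motivation is limited to weeks -3, -2 and 0.
3. At post-quit visits, report motivation descriptively by arm and by smoking status at the visit, with the abstinent proportion alongside. Draw no between-arm conclusion on motivation from those visits.

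A rank test placing abstinence above every motivation score is a tempting way to keep a formal post-quit test. It is not advised. With no true difference in motivation it rejected in 10-17% of simulated trials at 10% vs 20%, because it largely repeats the cessation outcome.

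The cost is a few sentences and no new data: motivation is collected before the quit date and smoking status is asked at every follow-up visit. The downside is that there is no formal long-term test of motivation.
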